1.0 Goals and Objectives (Scientific Aims)

The most common and effective treatment for cancer is surgery. By definition, surgical procedures are invasive; patients experience an abrupt decline in functional capacity after surgery. In addition to postoperative functional declines, patients experience an increase in symptoms, such as pain, fatigue, and distress.¹⁻³ Postoperatively, these symptoms contribute to a dramatic decline in quality of life (QOL).⁴⁻⁶ Postoperative recovery challenges are compounded by healthcare systems-related trends, including pressures to reduce readmissions and earlier postoperative discharge. As a result, the majority of postoperative care and recovery takes place at home. After hospital discharge, physical function can decline severely and symptoms can progress before the surgical team is notified.

A promising approach to early identification of post-discharge complications is through remote, real-time perioperative telemonitoring of functional activity and patient-reported outcomes (PROs). The approach can identify patients at risk for post-discharge complications, treat symptoms/complications in a real-time fashion, and prevent readmissions. The overall purpose of this study is to conduct a multi-site, comparative effectiveness, randomized controlled trial of perioperative telemonitoring for functional recovery in 438 English and Spanish-speaking cancer patients (398 for the main trial, 40 for the focus groups) scheduled to undergo major abdominal surgery (GI, GU, GYN). The program will be implemented at three geographically diverse sites in the Greater Los Angeles area, including one serving a low resource, socioeconomically-disadvantaged population. Accordingly, we propose the following specific aims:

Aim 1: Compare the impact of remote perioperative telemonitoring care versus surgeon only perioperative care on clinically significant changes in functional recovery (accelerometer daily step count) and related secondary patient-centered outcomes (sleep, sedentary time, symptom severity, symptom interference with daily activities).

Hypothesis: Remote perioperative telemonitoring improves functional recovery after major abdominal surgery.

Aim 2: Compare the impact of remote perioperative telemonitoring care versus surgeon only perioperative care on postoperative complications (Comprehensive Complications Index – CCI) and related secondary surgical outcomes (hospital readmission).

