Hypothesis: Remote perioperative telemonitoring reduces postoperative complications in the 30 days after major abdominal cancer surgery.

Aim 3: Compare early withdrawal (dropout or loss of accelerometer device) between the comparators.

Hypothesis: Remote perioperative telemonitoring does not excessively burden patients and families.

Aim 4: Explore perioperative telemonitoring care-related experiences (acceptability, technology usability, uptake/integration) among patients, families, and surgeons/nurses through qualitative focus groups and open-ended exit surveys.

Research Question: What are the various stakeholder's perspectives on remote perioperative telemonitoring care?

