10.0 Study Calendar

Table 4. Outcome Measures by Aims and Assessment Time Points

	Measures	Before Surgery (T1)	Pre-Discharge (T2)	Day 7 (T3)	Day 14 (T4)	Day 30 (T5)	Day 60 (T6)	Day 90 (T7)
Preop Functional Assessment	6 Minute Walking Time (6MWT)	X						
	Timed Up and Go (TUG)	X						
	Short Physical Performance Battery (SPPB)	X						
Aim 1	Functional Recovery (steps taken, sedentary time)	X	X	X	X	X	X	X
	General Symptoms - MD Anderson Symptom Inventory (MDASI)	X	X	X	X	X	X	X
Aim 2	Post-Operative Complications – CCI		X	X	X	X	X	X
	Hospital Readmissions			X	X	X	X	X
Aim 3	Early withdrawal (dropout, loss of device)							Throughout the Study
Aim 4	Open-Ended Patient Exit Survey							X
	Patients/Families/Surgeon/Nurses Experience – Focus Groups							Year 2-3, Month 22-30

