MD Anderson Symptom Inventory (MDASI) - The MDASI is a validated measure of 13 common cancer-related symptoms: pain, fatigue, nausea, sleep, distress/anxiety, shortness of breath, memory, appetite, dry mouth, drowsiness, sadness, vomiting, and numbness/tingling. Each symptom's severity is rated on a 10-point scale. A score of 1-3 indicates mild intensity, and 4-10 moderate to severe intensity. Patients also rate how much their symptoms interfered with 6 common functional domains: walking, activity, working/housework, social relationships, enjoyment of life, and mood. A movement of 1.2 points is clinically meaningful. The MDASI has been validated in surgical populations; Cronbach Alpha reliability ranges from 0.82 to 0.94.^{46, 83}

Functional Activity (Actigraph) – Based on published recommendations on best practice in use of accelerometry⁸⁴⁻⁸⁷, we will initiate several parameters to ensure that the data captured is reliable. First, data will be collected in 1 second epochs and reintegrated to 60 second epochs for analysis. Non-wear time will be defined as 60 minutes of continuous 0 counts. A minimum of 4 weekdays and 1 weekend day with at least 600 minutes (10 hours) of daily wear time will be considered valid. In order to be considered a valid day, patients need to wear the accelerometer for at least 10 waking hours (600 minutes). Data capture will focus on the following: 1) number of steps taken per day and 2) sedentary time. Recommended activity counts per minute (cpm) cutpoints will be used to categorize sedentary time (<100 cpm) from light-intensity physical activity (100–1951 cpm) and moderate/vigorous intensity physical activity (≥ 1952 cpm).

Comprehensive Complications Index (CCI) - The CCI[®] summarizes the entire patient postoperative experience with respect to complications (on a scale from 0 to 100), and is based on the established Clavien-Dindo classification. The CCI[®] was validated in a study with 1299 participants, and external validity was tested in a randomized trial evaluating pancreas, esophageal, and colon resections.^{88, 89}

Readmissions - Electronic health record audits will capture: 1) 30, 60, and 90 day inpatient readmissions, 2) reasons for readmissions, and 3) ER visits. If the patient seeks emergent care outside of the primary institution, the patient's permission will be obtained to review these records.

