13.0 Statistical Considerations

13.1 Study Design

This is a prospective, randomized, mixed methods, comparative effectiveness trial (1:1 randomization) of perioperative telemonitoring in cancer surgery (GI, GU, GYN). These cancer sites were selected because the surgical procedures, extent of resection, and expected surgical outcomes are similar. Our CER question is: What are the comparative effectiveness of remote perioperative telemonitoring care as compared to the surgeon (and surgical team) only perioperative care? This research focuses on comparing the two groups to identify which approach will most benefit cancer surgery patients.

In Aim 1, clinically significant changes in functional recovery (accelerometer daily step count) and related secondary patient-centered outcomes (sleep, sedentary time, symptoms, symptom interference with activity) will be tested over time by the comparators (remote perioperative telemonitoring care versus surgeon only perioperative care). The **primary outcome** is the clinically significant change in accelerometer daily step count over time. In Aim 2, we will test changes in postoperative complications and related secondary surgical outcomes (hospital readmissions) by the comparators. Here, the **primary outcome** is postoperative complications in the 30 days after surgery. In Aim 3, we will compare early withdrawal (dropout, loss of device) between the comparators. Finally, in Aim 4, we will qualitatively explore the perioperative telemonitoring experience from the patients, families, and surgeon's/nurse's perspective. This aim was included to explore perioperative care-related experiences (acceptability, technology usability, uptake/integration) among patients, families, and surgeons/nurses through qualitative focus groups and open-ended exit surveys. The data will be used to refine and assure model fidelity in future studies. It will also guide future integration into other healthcare system settings.

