Heterogeneity of Treatment Effect - Exploratory use of interaction terms will assess whether significant effects of the study intervention differ by sex or by age (i.e., above vs below 70 years). If found to be present, any such heterogeneity of treatment effect, not having been hypothesized in advance, will be reported as a preliminary finding that awaits confirmation in future studies.

Internal/External Validity and Avoidance of Bias - To limit possible confounding of the primary results, analyses of the prespecified hypotheses will be adjusted for covariates (age, sex, physical fitness at pre-surgical baseline). To assess the representativeness of study participants, their demographic characteristics (sex, age) will be compared to those of eligible patients who are approached for consent but decline to participate in the study. Our digital engagement platform will initiate reminder systems to reduce loss to follow-up.

Statistical Methods by Study Aims - Characteristics considered as potential covariates in all analyses will be age, sex, surgical technique, residential setting, and physical fitness at preoperative baseline. Any covariate that improves the model's fit to the observed data will be retained in the final analysis.

The analyses for Aims 1-3 will be by intention to treat (ITT); the ITT population will include all subjects who have given informed consent, been randomized to intervention or control arm, and undergone the planned cancer surgery.

Aim 1 – Allowing for an anticipated 20% attrition in use of accelerometer by Day 14 across both trial arms, an initial sample size of 332 (randomized 1:1) will provide (per East 6.5 software)

80% power to detect the hypothesized 14% difference in slope due to study intervention, using a 1-sided, repeated measures-difference of slope test with alpha=0.025.

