The Aim's primary endpoint will be the percent change from preoperative baseline in daily step count during the first 2 weeks post-discharge from hospital (measured on Discharge Day, Day +7, and Day +14). percent change from preoperative baseline in daily step count during the first 2 weeks post-discharge from hospital (measured on Discharge Day, Day +7, and Day +14). To recognize that these data may be missing not at random (ie, due to adverse event, distress, or withdrawal of consent), the effect of study intervention on primary endpoint will be modeled jointly with early withdrawal from data collection of that endpoint. Within the joint model, the sub-model for the primary endpoint will use generalized linear mixed modeling (with treatment and covariates as fixed factors, patient ID as random factor), while the other sub-model will analyze time to early withdrawal (Aim 3's primary endpoint) using proportional hazards regression. Similar joint modeling will be carried out for Aim 1's secondary endpoints (change from baseline in sedentary time, general symptoms, disease-specific symptoms).

Aim 2 – Because the CCI is derived from data routinely entered in the medical chart, no loss to follow-up is anticipated for this endpoint. A sample size of 332 subjects randomized 1:1 will provide (per East 6.5 software) 88% power to detect the hypothesized CCI benefit, using a 1-sided test of proportions, unpooled estimate of variance, critical p-value for efficacy=0.024, cumulative alpha=0.025.

The Aim's primary endpoint will be maximum Comprehensive Complications Index (CCI) during the 30 days post-discharge. Maximum CCI will be categorized as above vs below 15, and logistic regression will be used to evaluate the effect of study intervention. The Aim's secondary endpoint, time to hospital readmission through 90 days, will be subjected to survival analysis, handling any early withdrawal from study as a competing endpoint.

Aim 3 - The trial's sample size of n=332 will provide (per SAS software, PROC POWER for two-sample comparison of proportions) at least 80% power.

Treatment will be evaluated for association with this Aim's primary endpoint, time to early withdrawal, using proportional hazards regression. This analysis will be generated as a sub-model of the joint modeling for Aim 1.

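### The Aim 2 primary endpoint is given two different 30-day windows, and an operated patient who is never discharged has no defined outcome under the analysis wording

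*Combined protocol and SAP*

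**What the plan says.** Four places state the Aim 2 period.

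- Section 1.0, Aim 2 hypothesis: telemonitoring "reduces postoperative complications in the 30 days after major abdominal cancer surgery".
- Section 13.1: the Aim 2 primary outcome "is postoperative complications in the 30 days after surgery".
- Section 13.2, Aim 2: the "primary endpoint will be maximum Comprehensive Complications Index (CCI) during the 30 days post-discharge", then split at 15 and analysed by logistic regression.
- Synopsis, Statistical Considerations, Aim 2: the same definition as Section 13.2.

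Other text bears on how to read these.

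- Section 3.1 expects 332 evaluable patients (166 per group) at 30 days post-discharge and ties the power for the primary endpoints to them.
- Section 5.1 and Table 4 in Section 10.0 number the follow-up visits from discharge. In Table 4 the row "Post-Operative Complications – CCI" is also marked at the pre-discharge visit (T2).
- Section 12.1.3 says the index "summarizes the entire patient postoperative experience with respect to complications".
- Section 13.2 defines the intention-to-treat set as patients who have consented, "been randomized to intervention or control arm, and undergone the planned cancer surgery".
- Section 13.2 adds: "Because the CCI is derived from data routinely entered in the medical chart, no loss to follow-up is anticipated for this endpoint".

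**The concern.** A window from surgery and a window from discharge have different start and end dates for any patient with an inpatient stay. The hypothesis and the analysis of a primary endpoint therefore describe different periods. Two analysts following the text could build different binary outcomes from the same chart. They could differ on the last day that counts and on whether a complication confined to the index stay counts at all.

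The second problem is the anchor. Membership of the analysis set is fixed by randomization and surgery, but the outcome clock starts at discharge. For a patient who dies in hospital or is not discharged, the clock never starts. Section 13.2 gives such a patient no category, so the choice could be made after the data are seen, and it concerns some of the sickest patients. Discharge occurs after randomization, and Section 5.1 has telemonitoring begin before surgery. Leaving undischarged patients out would thus select on an event that the intervention could affect.

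**Working it through.** **1. The two windows compared.** Take surgery as day 0 and length of stay as L days. The window from surgery ends on day 30. The window from discharge starts on day L and ends on day 30 + L. The two share 30 − L days. The documents give no length of stay for this population, so L is assumed.

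| Assumed L | Post-discharge window ends on day | Days shared |
|---|---|---|
| 3 | 33 | 27 |
| 7 | 37 | 23 |
| 14 | 44 | 16 |

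With L = 7, a complication on postoperative day 33 counts only in the post-discharge window. One confined to day 3 lies in the surgery window. It reaches the post-discharge endpoint only if the index is carried forward cumulatively from surgery, which the plan does not say for this endpoint.

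**2. Patients without a window.** The intention-to-treat set is everyone randomized and operated, so at most 398 (199 per arm). The 332 in Section 3.1 are patients with complete data at 30 days post-discharge, so they are not the right base here. The share who die in hospital or are not discharged is not given. Assuming 1%, 3% or 5%:

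398 × 0.01 = 3.98; 398 × 0.03 = 11.94; 398 × 0.05 = 19.9. That is about 4, 12 or 20 patients.

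**3. The plan's 88% power.** This cannot be reproduced, because Section 13.2 states no rate of CCI above 15 in either arm. Its other inputs are 166 per arm, a one-sided test, unpooled variance and a critical p of 0.024 (z = 1.977). The formula is

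power = Φ( (p1 − p2) / √[p1(1 − p1)/n + p2(1 − p2)/n] − 1.977 ).

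Solved backwards for 88%, it fits 20% vs 8.1%, 30% vs 15.7%, 40% vs 24.1%, 50% vs 33.2% or 60% vs 43.0%. These are differences of 11.9 to 17.0 points.

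**4. Power if the undefined patients are dropped, rates unchanged.** At 88% power the standardized difference is 1.175 + 1.977 = 3.152. Dropping a fraction d multiplies it by √(1 − d):

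- d = 0.01: Φ(3.152 × √0.99 − 1.977) = 87.7%
- d = 0.03: Φ(3.152 × √0.97 − 1.977) = 87.0%
- d = 0.05: Φ(3.152 × √0.95 − 1.977) = 86.3%

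**5. Can the handling change the conclusion?** The example assumes 166 per arm and 10 undefined patients. Among the rest, CCI is above 15 in 48 control and 31 telemonitoring patients. The test is the unadjusted one-sided z test with unpooled variance; the planned logistic regression with covariates would differ somewhat.

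| Split, control / telemonitoring | Dropped | Counted as events | Counted as non-events |
|---|---|---|---|
| 4 / 6 | 48/162 vs 31/160, p = 0.016 | 52/166 vs 37/166, p = 0.031 | 48/166 vs 31/166, p = 0.014 |
| 5 / 5 | 48/161 vs 31/161, p = 0.013 | 53/166 vs 36/166, p = 0.017 | same, p = 0.014 |
| 6 / 4 | 48/160 vs 31/162, p = 0.011 | 54/166 vs 35/166, p = 0.009 | same, p = 0.014 |

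Only one cell crosses 0.024. The example is near the boundary by construction: 48/166 − 31/166 = 10.2 points, which has about 59% power. With 3 undefined patients instead of 10, only a 0/3 split counted as events crosses (48/166 vs 34/166, p = 0.037).

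**The case against.** The strongest reply is that the intended window is clear. Both places that specify the analysis say post-discharge, Section 3.1 ties evaluability and power to the same point, and follow-up visits are counted from discharge. The rationale in Section 1.0 concerns "early identification of post-discharge complications". On this view the hypothesis and Section 13.1 are loosely worded. This largely stands as an account of intent. It does not remove the contradiction, since Section 13.1 expressly labels the surgery-based period as the primary outcome.

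A second reply is that the index covers the whole postoperative course, is scored before discharge and comes from the chart, so a cumulative score could give every patient a value. That is plausible but not stated for this endpoint, and the end date would still differ from the hypothesis. The expectation of no loss to follow-up concerns the availability of data. It does not define an outcome for a window that never opens.

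A third reply is that the numerical effect is small. That stands.

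A reader might go further and infer that index-stay complications are definitely excluded, that undischarged patients will be dropped, that power is materially reduced, or that only a window starting at surgery is acceptable. The documents do not support any of these. The first two are open questions in the text, and the power loss in the check is under 2 points. A deliberate post-discharge endpoint fits the stated rationale.

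**Conclusion.** The point holds as an internal contradiction over a primary endpoint together with a missing analysis rule. It needs correcting because a primary endpoint should be fixed before outcomes are seen, not because a large numerical effect has been shown. Post-discharge is probably the intended window.

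On the assumed 1% to 5%, about 4 to 20 of up to 398 patients would have no defined outcome. In the worked example, their handling changes the conclusion only when the split between arms is uneven and the result lies near 0.024. How many patients would change category because of the window itself cannot be estimated, since the documents give neither length of stay nor the timing of complications. For the same reason, the size and direction of any change in power from switching windows are unknown.

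**What to change.** The sponsor chooses one window and makes three wording changes.

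1. State that window identically in the synopsis, the Aim 2 hypothesis in Section 1.0, Section 13.1 and Section 13.2.
2. State whether complications before discharge, including the T2 score, count toward the maximum.
3. Add one analysis rule that gives every intention-to-treat patient an outcome, including those who die in hospital or are not discharged. Two examples would do: a window that starts at surgery, or counting in-hospital death as CCI above 15 with a fixed cut-off date for patients not discharged.

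Then confirm that the 88% power refers to the chosen window, or restate it.

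The cost is protocol and SAP wording and, if needed, one power calculation. The synopsis already lists date of surgery, postoperative events and discharge date among the data collected. If the window starts at surgery, complications must be abstracted with their dates, because the scheduled Day 30 is counted from discharge. The restated power may be slightly lower.

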438 Patients (398 patients for the main trial, 40 for focus groups)
Estimated Duration of the Study
40 months
Summary of Subject Eligibility Criteria:
Study eligibility criteria include: 
 • Cancer patients scheduled to undergo major abdominal surgery for GI, GU, or GYN malignancies or presumed GI, GU, or GYN malignancies (as determined by surgeons); • Ability to read and understand English or Spanish, and • Age 18 years or older
Investigational Product Dosage and Administration:
NA
Clinical Observations and Tests to be Performed:
Diagnosis, tumor stage, neoadjuvant treatments, Charlson-Deyo co-morbidity index, time to adjuvant treatment, pre-op Zubrod/ECOG performance score, name of procedure, open or minimally invasive, ASA classification, date of surgery, post-op admission status and date, ICU days, post-operative events, discharge date, discharge status, preop objective functional measures (6-Minute Walking Test, Timed Up and Go, Short Physical Performance Battery).
Statistical Considerations:

Aim 1 - The Aim's primary endpoint will be the percent change from preoperative baseline in daily step count during the first 2 weeks post-discharge from hospital (measured on Discharge Day, Day +7, and Day +14). To recognize that these data may be missing not at random (ie, due to adverse event, distress, or withdrawal of consent), the effect of study intervention on primary endpoint will be modeled jointly with early withdrawal from data collection of that endpoint. Within the joint model, the sub-model for the primary endpoint will use generalized linear mixed modeling (with treatment and covariates as fixed factors, patient ID as random factor), while the other sub-model will analyze time to early withdrawal (Aim 3's primary endpoint) using proportional hazards regression. Similar joint modeling will be carried out for Aim 1's secondary endpoints (change from baseline in sedentary time, general symptoms, disease-specific symptoms).
 
Aim 2 - The Aim's primary endpoint will be maximum Comprehensive Complications Index (CCI) during the 30 days post-discharge. Maximum CCI will be categorized as above vs below 15, and logistic regression will be used to evaluate the effect of study intervention. The Aim's secondary endpoint, time to hospital readmission through 90 days, will be subjected to survival analysis, handling any early withdrawal from study as a competing endpoint.

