5.3 Criteria for Removal from Treatment

The only criterion for disenrollment is if participants desire to discontinue with study participation.

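### Early withdrawal is treated as a competing event for 90-day readmission and death is not mentioned; cumulative incidence would be too low, and the treatment comparison can also be biased

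*Combined protocol and SAP*

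**What the plan says.** The synopsis (Statistical Considerations, Aim 2) and section 13.2 give the same rule for the secondary endpoint: "time to hospital readmission through 90 days, will be subjected to survival analysis, handling any early withdrawal from study as a competing endpoint". No estimator, model or test is named. Death does not appear in this analysis or anywhere else in section 13.2; mortality is mentioned only as background in section 2.1.

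Other places bear on the rule:

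- **Data source.** Section 12.1.3 states "Electronic health record audits will capture: 1) 30, 60, and 90 day inpatient readmissions". For emergency care sought at another institution, the patient's "permission will be obtained to review these records".
- **The other chart-based Aim 2 endpoint.** Section 13.2 says of the complications index: "Because the CCI is derived from data routinely entered in the medical chart, no loss to follow-up is anticipated for this endpoint".
- **Analysis population.** Section 13.2 analyses Aims 1 to 3 by intention to treat, in all consented and randomized patients who had the planned surgery.
- **Meaning of withdrawal.** Section 5.3 says "The only criterion for disenrollment is if participants desire to discontinue with study participation". Aim 3 in section 1.0 is wider: "Compare early withdrawal (dropout or loss of accelerometer device) between the comparators". For Aim 1, section 13.2 uses another phrase again; the step-count endpoint is "modeled jointly with early withdrawal from data collection of that endpoint".

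**The concern.** A competing event is one after which the outcome can no longer occur. Withdrawal is not such an event for readmission; at most it is a reason for censoring, and only if the record can no longer be read. Death without readmission is such an event and is left out.

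Two things are at stake. First, a cumulative incidence that counts withdrawal as competing answers a different question: the chance of being readmitted before withdrawing. It cannot exceed the 90-day readmission risk, and it falls below that risk whenever a withdrawn patient is later readmitted. Second, the comparison between arms may be distorted. Whether it is, and by how much, depends on the estimator, on whether withdrawal is equal between arms, and on whether patients who withdraw have a different readmission risk from those who stay.

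**Working it through.** The plan gives no event rate, power or effect size for readmission, so there is no figure to reproduce. The check is an illustration.

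**Inputs from the documents**
- 90-day readmission after major cancer surgery: 23–43% (section 2.1). I use 30% as a value inside that range.
- Attrition: 20%, linked to evaluable data at 30 days (section 3.1), and 20% in accelerometer use by day 14 (section 13.2, Aim 1). Neither is a 90-day rate of leaving the study, and neither is split by arm.
- 332 patients, 166 per arm (section 3.1).

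**Assumptions**
- Withdrawal rates over 90 days; constant hazards; withdrawal independent of readmission unless stated.
- A true risk of 20% with telemonitoring where an effect is assumed.
- A one-sided 0.025 level, borrowed from the primary tests because none is stated for this endpoint.

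**1. Cumulative incidence, withdrawal spread over 90 days**

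Let a = −ln(1 − readmission risk) and b = −ln(1 − withdrawal risk). Then the reported value is a/(a+b) × [1 − exp(−(a+b))].

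- True 30%, withdrawal 20%: a = 0.3567, b = 0.2231. 0.3567/0.5798 × (1 − 0.7 × 0.8) = 0.6152 × 0.44 = **27.1%**.
- True 20%, withdrawal 20%: a = b, so 0.5 × (1 − 0.8 × 0.8) = 18.0%.
- A true difference of 10.0 points is therefore reported as 27.1 − 18.0 = **9.1 points**, with equal withdrawal.
- True 23% becomes 20.7%, and true 43% becomes 38.9%.
- True 30% with only 5% withdrawal: 0.8743 × (1 − 0.7 × 0.95) = 29.3%.

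**2. The same, with all withdrawal by day 14**

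Let h1 = a/90 and h2 = b/14. The reported value is h1/(h1+h2) × [1 − exp(−14(h1+h2))] + exp(−14(h1+h2)) × [1 − exp(−76 h1)].

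- True 30%, withdrawal 20%: h1 = 0.003963, h2 = 0.015939. 0.1991 × 0.2432 + 0.7568 × 0.2601 = 0.0484 + 0.1968 = **24.5%**.
- True 20%, withdrawal 20%: h1 = 0.002479. 0.1346 × 0.2273 + 0.7727 × 0.1717 = 0.0306 + 0.1327 = 16.3%.
- The 10-point difference becomes 24.5 − 16.3 = **8.2 points**.

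**3. Treatment comparison: one example, no true effect, risk 30% in both arms**

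Assume 25% withdrawal with telemonitoring and 15% with control, spread over 90 days.

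- The formula in step 1 gives 26.3% against 27.8%, a false difference of 1.5 points.
- Fine-Gray (withdrawn patients kept in the risk set to day 90): ln(1 − 0.263)/ln(1 − 0.278) is about 0.94, and simulation also gives 0.94. False positives at 166 per arm are about 5% instead of 2.5%.
- If control withdraws more (telemonitoring 15%, control 25%), the hazard ratio is 1.07 and false positives are 1.2%: the test turns conservative.
- A cause-specific Cox model censored at withdrawal stays at 1.00 and near the nominal error.
- With 20% in both arms, both methods give about 1.00.

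**4. Informative withdrawal, no true effect**

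Assume half the patients have four times the readmission hazard and four times the withdrawal hazard.

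- 25% against 15% withdrawal: the censored Cox hazard ratio is 0.976 and Fine-Gray gives 0.92.
- Equal 20% withdrawal, informative in the telemonitoring arm only: the Cox hazard ratio is 0.961 and Fine-Gray 0.964.

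**5. After the fix**

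With record-captured readmissions counted after withdrawal, the estimate returns to 30.0% and hazard ratios under no effect are about 1.00 in all these patterns.

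The effect of omitting death cannot be computed, because the documents give no mortality assumption for this trial.

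**The case against.** The strongest reply has four parts.

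- **The plan says only survival analysis.** Under a cause-specific hazard model, a competing event is handled exactly as censoring, so the label may do no harm. This stands in part: with non-informative withdrawal the Cox comparison is sound. Any cumulative incidence reported beside it would still be too low, and with informative withdrawal the censored Cox model is biased too. Section 13.2 itself allows, for Aim 1, that data may be missing not at random.
- **The withdrawal rates are hypothetical.** This stands. No 90-day rate is given, and at 5% the shortfall at a true 30% is only 0.7 points (30.0 − 29.3).
- **Some readmissions really are lost after withdrawal.** This stands in part. Outside records need permission, and the expectation of no loss for the complications index covers 30 days, not 90. That is a reason to censor when record access ends, not to call withdrawal a competing event.
- **Follow-up is clear enough.** This stands as to the time origin: section 5.2 and the study calendar (section 10.0) count from discharge, so I raise no complaint there.

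A reader might also infer that losing the accelerometer ends readmission follow-up. The documents do not establish this. The readmission sentence speaks of withdrawal from the study, which section 5.3 ties to the patient's wish to stop. Aim 3's wider definition leaves the other reading open, which is why the fix settles it.

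**Conclusion.** The rule is wrong as written and should be replaced. A cumulative incidence reported under it is too low whenever a withdrawn patient is later readmitted. At an assumed 20% independent withdrawal in both arms, 30% becomes 27.1% or 24.5% depending on timing, and a 10-point difference becomes 9.1 or 8.2 points.

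Bias in the treatment comparison is possible but conditional. Two stronger readings should be avoided. A reader might infer that the trial will falsely favour telemonitoring; the documents do not predict unequal withdrawal (Aim 3 is there to test it), and the direction reverses if control patients withdraw more. A reader might instead infer that bias needs both unequal withdrawal and Fine-Gray or Gray's test; steps 1, 2 and 4 show otherwise, since the risk difference shrinks with equal withdrawal and informative withdrawal also affects a censored Cox model. Nor is the day-14 result a worst case: independence is assumed there, and informative withdrawal can lower the estimate further.

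This is a secondary endpoint with no stated alpha or power, so the change is one that should be made; it does not touch the primary analyses.

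**What to change.** In the synopsis (Aim 2) and section 13.2 (Aim 2), replace the rule "handling any early withdrawal from study as a competing endpoint" and the sentence that contains it with:

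> Time from discharge to first inpatient readmission through day 90 is taken from the health record for all ITT patients discharged alive, whether or not they still use the app or accelerometer; device loss is not withdrawal for this endpoint. Death without readmission is the competing event. Patients are censored only at day 90 or when record access ends. The treatment effect is the cause-specific hazard ratio from a Cox model, with Aalen-Johansen cumulative incidence by arm. A sensitivity analysis addresses informative censoring and outside readmissions that cannot be captured.

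The cost is the change of wording and a little more analysis; the record audits are already planned. The sponsor should check that the consent text, which is not in the reviewed pages, allows record review, including outside records, after app or device use stops.
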